Clinical Trial Protocol

Document Number: c12098812-09

EudraCT No.: 2016-003470-40

BI Trial No.: 1371-0001

BI Investigational Product: BI 894416

Title: Safety, tolerability, pharmacokinetics and pharmacodynamics of single rising oral doses of BI 894416 in healthy male subjects (single-blind, partially randomised, placebo-controlled parallel group design)

Lay Title: This study in healthy men tests how different doses of BI 894416 are taken up in the body and how well BI 894416 is tolerated

Clinical Phase: I

Trial Clinical Monitor:

Phone:

Fax:

Principal Investigator:

Phone:

Fax:

Status: Final Protocol (Revised Protocol (based on global amendment 8))

Version and Date: Version: 9.0 Date: 25 Jul 2018

Page 1 of 122

Proprietary confidential information

© 2018 Boehringer Ingelheim International GmbH or one or more of its affiliated companies. All rights reserved.
This document may not – in full or in part – be passed on, reproduced, published or otherwise used without prior written permission

Proprietary confidential information © 2018 Boehringer Ingelheim International GmbH or one or more of its affiliated companies

CLINICAL TRIAL PROTOCOL SYNOPSIS

Name of company: Boehringer Ingelheim		Tabulated Trial Protocol		
Name of finished product: Not applicable				
Name of active ingredient: BI 894416				
Protocol date: 09 AUG 2017	Trial number: 1371-0001		Revision date: 25 JUL 2018	
Title of trial: Safety, tolerability, pharmacokinetics and pharmacodynamics of single rising oral doses of BI 894416 in healthy male subjects (single-blind, partially randomised, placebo-controlled parallel group design)				
Principal Investigator:				
Trial site:				
Clinical phase:	I			
Objectives:	To investigate safety, tolerability, pharmacokinetics and pharmacodynamics following single rising doses of BI 894416, to obtain pharmacokinetic data of BI 894416 after administration as tablet formulation and to investigate relative bioavailability of a tablet formulation as compared to oral solution			
Methodology:	1) Single rising dose (SRD) part: Single-blind, partially randomised within dose groups, placebo-controlled, parallel-group design 2) Relative bioavailability (rel BA) part: Open-label, randomised two-way crossover followed by a fixed sequence design			
No. of subjects:				
total entered:	76*			
each treatment:	1) SRD part: 8 per dose group (6 on active drug and 2 on placebo) * Additional subjects may be entered in the SRD part to allow testing of additional doses on the basis of experience gained during the trial conduct (e.g., preliminary PK data), provided the planned and approved highest dose will not be exceeded. Thus, the actual number of subjects entered in the SRD part may exceed 64 (may exceed 76 subjects total entered into the trial), but will not exceed 80 subjects entered in the SRD part (will not exceed 92 subjects total entered). 2) Rel BA part: 12 (all on active drug)			
Diagnosis:	Not applicable			
Main criteria for inclusion:	Healthy male subjects, age of 18 to 45 years, body mass index (BMI) of 18.5 to 29.9 kg/m ²			

Proprietary confidential information © 2018 Boehringer Ingelheim International GmbH or one or more of its affiliated companies

Name of company: Boehringer Ingelheim		Tabulated Trial Protocol		
Name of finished product: Not applicable				
Name of active ingredient: BI 894416				
Protocol date: 09 AUG 2017	Trial number: 1371-0001		Revision date: 25 JUL 2018	
Test products:		1) SRD part: BI 894416 as a powder for oral solution (PfOS		
		2) Rel BA part: BI 894416 as a tablet formulation (10 mg)		
dose:		1) SRD part: 3 mg, 10 mg, 20 mg, 40 mg, 54 mg (interim dose 30 mg (interim dose), 70 mg, 110 mg, 160 mg, 220 mg		
		2) Rel BA part: 10 mg (1 tablet; treatment X; in period 1 or 2), 40 mg (4 tablets; treatment Z; in period 3)		
mode of admin.: Oral with 240 mL of water after an overnight fast of at least 10 h				
Comparator product:		1) SRD part: Placebo solution 2) Rel BA part: BI 894416 as a powder for oral solution (PfOS		
dose:		1) SRD part: Not applicable 2) Rel BA part: 10 mg (treatment Y; in period 1 or 2)		
mode of admin.: Oral with 240 mL of water after an overnight fast of at least 10 h				
Duration of treatment:		1) SRD part: One single dose per subject 2) Rel BA part: One single dose per subject in each treatment period (3 single doses in total		
Criteria for pharmacokinetics:		1) SRD part: Secondary endpoints: $AUC_{0-\infty}$ and C_{max} of BI 894416		
		2) Rel BA part: Secondary endpoints: AUC_{0-tz} , $AUC_{0-\infty}$ and C_{max} of BI 894416		

Name of company: Boehringer Ingelheim		Tabulated Trial Protocol	
Name of finished product: Not applicable			
Name of active ingredient: BI 894416			
Protocol date: 09 AUG 2017	Trial number: 1371-0001		Revision date: 25 JUL 2018
Criteria for safety:	
1) SRD part: Primary endpoint to assess safety and tolerability of BI 894416 is the number [N (%)] of subjects with drug-related adverse events.
 
2) Rel BA part:
		
Statistical methods:	
1) SRD part: Descriptive statistics for safety, PK calculated.
 
2) Rel BA part: Relative bioavailability will be estimated by the ratios of the geometric means (tablet 10 mg / PfOS 10 mg) for the secondary endpoints. Additionally, the two-sided 90% confidence intervals (CIs) will be provided. This method corresponds to the two one-sided t-tests procedure, each at the 5% significance level. Since the main focus is on estimation and not testing, an acceptance range was not specified. The statistical model will be an ANOVA on the logarithmic scale including effects for 'sequence', 'subjects nested within sequences', 'period' and 'treatment'. CIs will be calculated based on the residual error from ANOVA.
 
Descriptive statistics will be calculated for all endpoints.
		

A 10x10 grid of lines on a white background, representing a 10x10 matrix. The grid consists of 10 vertical lines and 10 horizontal lines, intersecting to form a 9x9 grid of squares. The lines are thin and black, set against a plain white background.

TABLE OF CONTENTS

3. DESCRIPTION OF DESIGN AND TRIAL POPULATION.....	43
3.1 OVERALL TRIAL DESIGN AND PLAN	43
3.1.1 Administrative structure of the trial.....	47
3.2 DISCUSSION OF TRIAL DESIGN, INCLUDING THE CHOICE OF CONTROL GROUP.....	48
3.3 SELECTION OF TRIAL POPULATION	49
3.3.1 Main diagnosis for study entry	49
3.3.2 Inclusion criteria	49
3.3.3 Exclusion criteria	49
3.3.4 Removal of subjects from therapy or assessments.....	51
3.3.4.1 Removal of individual subjects.....	51
3.3.4.2 Discontinuation of the trial by the sponsor	52
3.3.5 Replacement of subjects	52
4. TREATMENTS.....	53
4.1 TREATMENTS TO BE ADMINISTERED	53
4.1.1 Identity of BI investigational product and comparator products	53
4.1.2 Method of assigning subjects to treatment groups	55
4.1.4 Drug assignment and administration of doses for each subject	55
4.1.5 Blinding and procedures for unblinding	57
4.1.5.1 Blinding.....	57
4.1.5.2 Procedures for emergency unblinding	57
4.1.6 Packaging, labelling, and re-supply	57
4.1.7 Storage conditions.....	58
4.1.8 Drug accountability	58
4.2 OTHER TREATMENTS, EMERGENCY PROCEDURES, RESTRICTIONS	59

2. RATIONALE, OBJECTIVES, AND BENEFIT - RISK ASSESSMENT

2.1 RATIONALE FOR PERFORMING THE TRIAL

This First-in-Man trial is intended to start the clinical development of BI 894416

Single-rising dose (SRD) part

Effects of single rising doses of BI 894416 on safety, tolerability, pharmacokinetics, and will be assessed in healthy male volunteers. Within each dose group, all actively treated individuals will receive the same dose of BI 894416. The next higher dose will only be administered if the treatment in the preceding group was safe and showed acceptable tolerability and if the estimated systemic exposure of the next dose (guided by preliminary PK analyses) does not exceed the maximum acceptable systemic exposure (for details see Sections [2.1.2](#), [2.1.3](#), [3.1](#), [3.3.4.2](#) and [7.3.4](#)).

Relative bioavailability (rel BA) part

Oral solution formulation of BI 894416 is used in the SRD part of the current trial, whereas further clinical trials with BI 894416 are planned for use with a tablet formulation. However, the relative bioavailability of BI 894416 as tablet formulation compared to oral solution is unknown. It is not excluded, that bioavailability of BI 894416 as tablet formulation may differ from oral solution. Therefore it is required to investigate relative bioavailability of BI 894416 as tablet formulation in comparison to oral solution, in order to plan the doses for further trials.

The rel BA part will be done after the 70 mg dose group was performed in the SRD part.

In the rel BA part, all subjects will be treated with 10 mg BI 894416 as tablet (treatment X) and as oral solution formulation (treatment Y) in a two-way randomized crossover fashion in visits 2 and 3 (periods 1 and 2, respectively). The resulting data will allow assessment of relative bioavailability at a dose of 10 mg.

After analysis of preliminary PK and safety data (see [Sections 3.1](#) and [7.3.4](#)), the subjects that participate in the rel BA part will be dosed in visit 4 (period 3) with 40 mg BI 894416 as tablets (treatment Z).

2.1.4 Exploration of relative bioavailability

For the rationale for the relative bioavailability (rel BA) part, please refer to [Section 2.1](#).

Following the 70 mg dose group in the SRD part, rel BA will be explored in the rel BA part. First, rel BA is investigated in two treatment periods (treatment X: tablet 10 mg; treatment Y: oral solution 10 mg) in an open-label, two-way, randomized crossover fashion.

Thereafter, subjects in the rel BA part will be treated in period 3 with 40 mg BI 894416 as tablets (treatment Z), if allowed after analysis of preliminary PK and safety data (see Sections [3.1](#) and [7.3.4](#)).

2.2 TRIAL OBJECTIVES

The primary objective of this trial is to investigate the safety and tolerability of BI 894416 in healthy male subjects following oral administration of single rising doses of 3 mg, 10 mg, 20 mg, 40 mg, 70 mg, 110 mg, 160 mg, and 220 mg.

Secondary objectives are the exploration of the pharmacokinetics (PK) including dose proportionality after single dosing of BI 894416 as oral solution, the investigation of PK of BI 894416 as tablet formulation and the exploration of relative bioavailability of BI 894416 as tablet formulation compared to oral solution.

A description of the endpoints to be determined, and the observations along with specific information as how to collect the data for that information, is provided in [Section 5](#).

3. DESCRIPTION OF DESIGN AND TRIAL POPULATION

3.1 OVERALL TRIAL DESIGN AND PLAN

The single-rising dose part of the trial is designed as single-blind, partially randomised, and placebo-controlled within parallel dose groups.

The relative bioavailability (rel BA) part of the trial is designed as open-label, two-way crossover followed by a fixed sequence.

A total of 76 healthy male subjects are planned to participate in the trial, thereof 64 in the SRD part and 12 in the rel BA part. Additional dose groups may be added to the SRD part (see below). Therefore the actual number of subjects entered into the trial may exceed 76, but will not exceed 92 subjects entered.

SRD part

A total of 64 healthy male subjects is planned to participate in the SRD trial part, according to 8 sequential groups comprising 8 subjects per group. However, additional subjects may be entered to allow testing of additional doses on the basis of experience gained during the trial conduct (e.g. preliminary PK data), provided the planned and approved highest dose will not be exceeded. Thus, the actual number of subjects entered into the SRD part may exceed 64, but will not exceed 80 subjects entered in the SRD part. Such changes may be implemented via non-substantial CTP Amendments.

Within each dose group, 6 subjects are planned to receive the active drug and 2 are planned to receive placebo. Only one dose is tested within each dose group. Each dose group will consist of 3 cohorts which will be treated subsequently for safety reasons. The 1st and 2nd cohorts will be treated in a fixed sequence and the 3rd cohort will be randomised.

The dose groups to be evaluated in the SRD part are outlined in Table 3.1: 1 below.

Table 3.1: 1 Dose groups of the SRD part

Dose Group	1	2	3	4	11*	9**	5	6	7	8
Dose [mg]	3	10	20	40	54	30	70	110	160	220
Number of subjects	8	8	8	8	8	8	8	8	8	8
Subjects receiving placebo	2	2	2	2	2	2	2	2	2	2
Subjects receiving active drug	6	6	6	6	6	6	6	6	6	6

* Interim dose group added with Global Amendment No. 4 following dose group 4

** Interim dose group added with Global Amendment No. 6 following interim dose group 11

Proprietary confidential information © 2018 Boehringer Ingelheim International GmbH or one or more of its affiliated companies

On the first study day of each dose level of the SRD part, the 1st cohort will be treated in the following order: First subject (active) followed at least 10 min later by the second subject (placebo).

The 2nd cohort will be treated not earlier than 22 hours later (minimum time interval between 1st subject of 1st cohort and 1st subject of 2nd cohort). In the 2nd cohort, a time interval of at least 10 min will be maintained between dosings of individual subjects (active – active).

The 3rd cohort will be treated not earlier than 46 hours later (minimum time interval between 1st subject of 2nd cohort and 1st subject of 3rd cohort). In the 3rd cohort, a time interval of at least 10 min will be maintained between dosings of individual subjects (3 active, 1 placebo; randomized order).

The dose groups of the SRD part will be investigated consecutively in ascending order of dose

The decision to proceed to the next dose group will be based upon the safety, tolerability, and pharmacokinetic data of the preceding dose groups. The next dose will only be given if, in the opinion of the investigator and the trial clinical monitor (or authorised deputies), no safety concerns arose in the preceding dose group (i.e. no dose-limiting events occurred) and if none of the pre-specified trial-specific stopping criteria were met (refer to [Section 3.3.4.2](#)).

A documented Safety Review must take place prior to each dose escalation. Furthermore, an unscheduled safety review meeting can be requested anytime for any reasonable cause by the Principal Investigator (or an authorised deputy) or the Sponsor of the study, e.g. because of any unforeseen adverse events, etc. Dose escalation will only be permitted if no safety concerns exist in the opinion of the Principal Investigator (or an authorised deputy) and the trial clinical monitor (or an authorised deputy).

The investigator is allowed to alter the scheduled dose levels (e.g. add low and/or intermediate dose levels) on the basis of experience gained during the study, provided the planned and approved highest dose is not exceeded. In this case, the total number of subjects in this trial might increase. The investigator and/or the sponsor should stop dose escalation in case the safety evaluation leads to concerns that would not allow higher dosing.

An overview of all relevant trial activities is provided in the [Flow Chart](#). For visit schedules and details of trial procedures at selected visits, refer to [Sections 6.1](#) and [6.2](#), respectively.

Rel BA part

A total of 12 healthy male subjects is planned to participate in the rel BA trial part.

The rel BA trial part will be started (i.e., dosing in rel BA part will be started) after availability of preliminary PK and safety data of the 70 mg dose group of the SRD trial part.

The rel BA part consists of three treatment periods, and all entered subjects are planned to participate at all three treatment periods. Treatments are open-label. In periods 1 and 2, the subjects will receive the treatments X (one single dose of 10 mg BI 894416, tablet formulation, fasting conditions) and Y (one single dose of 10 mg BI 894416, oral solution formulation, fasting conditions) in a randomized two-way crossover fashion. These two periods are followed, after documented review of PK and safety data of periods 1 and 2 of the rel BA part, by treatment Z (one single dose of 40 mg BI 894416, tablet formulation, fasting conditions).

The subjects will be randomly allocated to the two treatment sequences (X-Y-Z or Y-X-Z).

The decision to start treatment in the rel BA part (i.e. to administer treatment in period 1) will be based upon the safety, tolerability, and pharmacokinetic data of the available dose groups of the SRD part including also the 70 mg dose group.

The decision to administer treatment in period 3 of the rel BA part will be based upon the safety, tolerability, and pharmacokinetic data of the SRD part including also the 70 mg dose group and of periods 1 and 2 of the rel BA part.

Proprietary confidential information © 2018 Boehringer Ingelheim International GmbH or one or more of its affiliated companies

Treatment in the rel BA part (i.e. treatment in period 1) will only be started if, in the opinion of the investigator and the trial clinical monitor (or authorised deputies), no safety concerns arose in the preceding dose groups of the SRD part (i.e. no dose-limiting events occurred) and if none of the pre-specified trial-specific stopping criteria were met (refer to [Section 3.3.4.2](#)).

Treatment in period 3 of the rel BA part will only be started if, in the opinion of the investigator and the trial clinical monitor (or authorised deputies), no safety concerns arose in the preceding dose groups of the SRD part or in periods 1 and 2 of the rel BA part (i.e. no dose-limiting events occurred) and if none of the pre-specified trial-specific stopping criteria were met (refer to [Section 3.3.4.2](#)).

If it is decided, based on the criteria above, that treatment in period 3 is not given, no further procedures in period 3 are to be done;

A documented Safety Review must take place prior to starting treatment in the rel BA part in periods 1 and 3. Furthermore, an unscheduled safety review meeting can be requested anytime for any reasonable cause by the Principal Investigator (or an authorised deputy) or the Sponsor of the study, e.g. because of any unforeseen adverse events, etc. Treatments will only be started if no safety concerns exist in the opinion of the Principal Investigator (or an authorised deputy) and the trial clinical monitor (or an authorised deputy).

The investigator and/or the sponsor should decide to stop treatment of subjects in the rel BA part in case the safety evaluation leads to concerns.

An overview of all relevant trial activities is provided in the [Flow Chart](#). For visit schedules and details of trial procedures at selected visits, refer to [Sections 6.1](#) and [6.2](#), respectively.

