7.3.4 Preliminary analyses

Preliminary PK analyses

In contrast to the final PK calculations, the preliminary analysis will be based on planned sampling times rather than on actual times, regardless of whether actual times were within the time windows or not. Therefore, minor deviations of preliminary and final results may occur. The preliminary analysis will provide individual and mean concentration-time profiles and summary statistics of individual values. The preliminary results will be distributed to the Investigator and the trial team.

Depending on the results of available preliminary PK analyses, the tolerability and safety of the compound, and changes of dosing schedule (e.g. additional intermediate doses) additional PK preliminary analysis may be performed based on the request of the Trial Clinical Monitor, the investigator, or Trial Clinical Pharmacokineticist. No formal preliminary PK report will be written.

SRD part

A preliminary analysis of PK parameters (AUC_{0-24} and C_{max} of BI 894416) provided as individual values and geometric means will be performed for each dose level before proceeding to the next level.

Proprietary confidential information © 2018 Boehringer Ingelheim International GmbH or one or more of its affiliated companies

Data from at least 4 actively dosed subjects at the current dose level (dose level N) are required in order to proceed to the next dose level (dose level N+1).

For escalation from Dose Group 1 to Dose Group 2, preliminary PK data are not required.

No inferential statistical interim analysis is planned. However, after each dose group the investigator (or his deputy) is allowed to postpone further dose progression until a preliminary analysis of the data already obtained has been performed.

Rel BA part

A preliminary analysis of PK parameters (AUC_{0-24} and C_{max} of BI 894416) provided as individual values and geometric means will be performed for the current dose group in the SRD part before proceeding to the rel BA part (i.e., before dosing of subjects in the rel BA part in period 1).

In addition, a preliminary analysis of PK parameters (AUC_{0-24} and C_{max} of BI 894416) of periods 1 and 2 of the rel BA part provided as individual values and geometric means will be performed before proceeding to dosing of subjects in period 3 of the rel BA part.

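### Does putting the 30 mg group between 54 mg and 70 mg let the 70 mg decision bypass the 54 mg data?

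*Protocol*

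**What the plan says.** Protocol 3.1 gives the order of the SRD groups as: "The dose groups of the SRD part will be investigated consecutively in ascending order of dose". Table 3.1: 1 lists the groups as "Dose Group 1 2 3 4 11* 9 5 6 7 8" with doses "Dose [mg] 3 10 20 40 54 30 70 110 160 220". The footnote for group 11 (54 mg) reads "Interim dose group added with Global Amendment No. 4 following dose group 4", and the footnote for group 9 (30 mg) reads "Interim dose group added with Global Amendment No. 6 following interim dose group 11". Section 7.6 repeats this sequence, and the synopsis lists the doses in the same order.

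Three passages govern escalation by reference to position in the sequence:

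- Section 2.1: "The next higher dose will only be administered if the treatment in the preceding group was safe and showed acceptable tolerability".
- Section 3.1: the next dose is given only if "no safety concerns arose in the preceding dose group (i.e. no dose-limiting events occurred", and only if no trial-specific stopping criterion has been met.
- Section 7.3.4: "Data from at least 4 actively dosed subjects at the current dose level (dose level N) are required" before moving to level N+1.

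Section 3.1 adds conditions that are not tied to a single group. The decision rests on the safety, tolerability and pharmacokinetic data of the earlier groups, in the plural. A documented safety review precedes every escalation. Escalation is allowed only if the investigator and the trial clinical monitor see no safety concern. The same section lets the investigator add low or intermediate dose levels below the approved maximum.

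**The concern.** The order sentence and the table cannot both describe the plan, because going from 54 mg to 30 mg is a step down. The look-back conditions appear to have been written for a sequence that only rises, where the group given last is also the next lower dose. For 70 mg the two differ: the group given last is 30 mg and the next lower dose is 54 mg.

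If the singular wording is applied to the 30-to-70 step alone, a clean 30 mg group would satisfy the safety condition and the minimum pharmacokinetic data for 70 mg. A signal at 54 mg would then not stand in the way. In a first-in-human trial that would matter, and the more so because the relative bioavailability part starts only after the 70 mg data are available.

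**Working it through.** **Inputs.** Dose sequence from Table 3.1: 1; group size of 8 (6 active, 2 placebo) from Table 3.1: 1; the SRD total of 80 from Section 7.6; the overall cap of 92 from Sections 3.1 and 7.6.

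**The plan's own count.** 10 groups × 8 = 80 SRD subjects, and 80 + 12 = 92 in total. Both match, so the two interim groups are fully built into the current plan.

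**Step sizes** (each dose divided by the one before it in the table):

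| Step (mg) | Ratio |
|---|---|
| 3 to 10 | 3.33 |
| 10 to 20 | 2.00 |
| 20 to 40 | 2.00 |
| 40 to 54 | 1.35 |
| 54 to 30 | 0.56 |
| 30 to 70 | 2.33 |
| 70 to 110 | 1.57 |
| 110 to 160 | 1.45 |
| 160 to 220 | 1.38 |

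There is one downward step. Relative to 54 mg, the highest dose given before it, 70 mg is 70/54 = 1.30-fold.

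**Does any consistent reading let 54 mg drop out?**

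1. *Preceding means order of administration.* The Section 3.1 condition governs every next dose. After 54 mg the next dose is 30 mg, so a concern at 54 mg stops the sequence at that point and 70 mg is never reached. Section 7.3.4 works the same way: at least 4 actively dosed subjects at 54 mg are needed before 30 mg, then at least 4 at 30 mg before 70 mg.
2. *Preceding means order of dose.* The group next below 70 mg is 54 mg, so both the safety condition and the pharmacokinetic minimum refer to 54 mg directly.

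Under either reading 54 mg has to pass. It escapes only if the order of administration is used for the step into 70 mg and ignored for the step into 30 mg.

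**Conditions that do not depend on the reading.** Section 3.1 takes in all earlier groups, requires the documented review and permits escalation only without safety concerns. In Section 3.3.4.2 the adverse-event and QT criteria are framed per dose level, whichever level that is, and a single drug-related serious adverse event is enough under the first criterion.

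**Relative bioavailability part.** The condition for starting it, in Section 3.1, refers to the preceding SRD groups in the plural, and the data basis names the 70 mg group. The position of the 30 mg group does not touch it.

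**Analysis.** SAP 6.1 and Table 6.1: 1 label the on-treatment phases by dose and pool all placebo subjects. The primary endpoint is summarised descriptively by treatment (SAP 7.8.1). None of these summaries uses the order in which the groups were run.

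**The case for a change.** The strongest counter-argument combines sections. Section 2.1 restricts only the next higher dose. Going from 54 to 30 mg is not upward, so on that wording it is unrestricted, and 70 mg is then checked against the preceding group, which in sequence is 30 mg. The parallel condition for the relative bioavailability part uses the plural, so a reader could infer that the singular in the SRD condition was deliberate. The term level N+1 is also not defined for a group run out of dose order.

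As a comment on drafting, this stands: no visible sentence says which group is the reference for 70 mg. As a comment on the decision, it does not. Section 2.1 is one condition among several, and Section 3.1 applies alongside it with a rule for every next dose, upward or not. Even if a concern at 54 mg were taken not to block a downward step, the plural data basis, the safety review and the requirement of no safety concern would still bring that concern into the 70 mg decision.

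The worry that exposure at 70 mg might be projected from 30 mg alone is not supported by the visible text. Section 2.1 speaks of preliminary pharmacokinetic analyses in the plural and points to Sections 2.1.2 and 2.1.3, which are not in the public version. The order sentence also has no full stop in the public text, so a qualifier may have been removed there. That cannot be settled either way.

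**Conclusion.** The mismatch is real: the order sentence in Section 3.1 disagrees with Table 3.1: 1, its footnotes and Section 7.6. As text, these passages have to be reconciled, and the singular references in Sections 2.1, 3.1 and 7.3.4 could be clearer for the out-of-order group. This is a clerical slip plus a small gap that the investigator and trial clinical monitor would fill sensibly. The footnotes disclose the order, and Section 3.1 foresees added low or intermediate doses.

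The safety consequence does not follow. Of the two step sizes, 2.33-fold and 1.30-fold, the larger would describe the decision only if the 54 mg data were set aside, and no consistent reading of the conditions does that. The same escalation decisions are reached, the start of the relative bioavailability part is unaffected, and no summary in the SAP changes.

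This rests on two assumptions: that the conditions in Sections 2.1, 3.1, 3.3.4.2 and 7.3.4 apply together, as they are written, and that nothing in the unavailable Sections 2.1.2 and 2.1.3 overrides them. No view is taken on which dose order or escalation rule is right.
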